Gene Expression: RNA will be extracted from 15-20 mg of muscle tissue according to protocol (Molecular Research Center, Inc, Cincinnati, OH). High quality RNA will be determined using lab-on-chip microfluidic technology automated nucleic acid electrophoresis and analysis. Total RNA will be reverse transcribed into cDNA using the iScript cDNA Synthesis Kit (Bio Rad, Hercules, CA) on a C1000 Thermal Cycler (Bio Rad, Hercules, CA). Determination of relative mRNA expression will be performed using a CFX96 Real-Time System coupled to a C1000 Thermal Cycler (Bio Rad, Hercules, CA) and Genomics Core facility NextSeq 500 at the University of Oregon.

Mitochondrial respiration. Oxidative phosphorylation rates in response to 50 μ M ADP will be determined in saponin permeabilized vastus lateralis biopsies (5-10 mg) using the two-channel high resolution respirometer (Oroboros Oxygraph; Innsbruck, Austria) with the saturating concentrations of the following substrate combinations [in mM]: pyruvate [5] + malate [5], palmitoylcarnitine [0.04] + malate [5], succinate [10] + 100 nM rotenone, or malate [5] + glutamate [10]. Respiration studies were performed at an initial oxygen concentration of 300 μ M at 37°C in MiR06 respiration buffer containing [in mM] EGTA [0.5], MgCl₂·6 H₂O [3], K-lactobionate [60], taurine [20], KH₂PO₄ [10], HEPES [20], sucrose [110], 1g/L BSA, 280U/ml catalase, pH 7.4 [with KOH].

Mitochondrial dysfunction may introduce sample bias as well as negatively impact short and longer-term function. To account for this, we propose to measure mitochondrial respiration using the Oroboros O2k respirometer, and normalize results statistically and use the non-operative leg as internal control.

Secondary Outcome Measures. Study Aim #1 will allow the team to collect preliminary functional outcome data to better inform the long-term study (Aim #2). The secondary outcome measures will be quantified using the following study activities and procedures:

- **Muscle volume.** The MRI unit is located at the Lewis Center for Neuroimaging (LCNI) on the University of Oregon campus. Should the MRI unit at LCNI be unavailable within study-specific assessment points (i.e. scheduling or mechanical issues), the MRI at the Slocum Center for Orthopedics will be utilized. In addition, patients in partnership with the study team, may elect to have all scans performed at the Slocum Center.

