All scans will be performed prior to strength & functional testing and a minimum of 24 hr post-therapy. T1 & T2 weighted MR images will be used to quantify quadriceps volume vs. edema. MRI is safe for TKA patients (implants are non-ferrous) and is ideally suited for muscle volume quantitation. Capture protocols will be stored on the unit to ensure accurate image collection over the course of the study. MRIs will not be performed in a fasting state.

MRIs performed at the Slocum Center will follow the standard operating procedures of Slocum MRI as per standard of care. Slocum MRI will carry out their own screening processes at the time of the scan. Research staff will alert MRI staff if the patient has any contraindicated implanted devices prior to the scan. Slocum MRI will follow their standard operating procedures to ensure MRI safety.

Because MRIs at the LCNI are strictly used for research purposes, study participants will complete the IRB-approved LCNI screening form in advance of their MRI procedure(s). Based on the screening form results if LCNI requires more information to comfortably scan our patients, LCNI will call the study coordinators. Information that may be requested by LCNI includes any of the following (more than one possible):

1. Confirmation of MRI scan with implant in question has occurred previously
2. Blinded operative notes of the implant in question
3. Advance conversation with the patient at LCNI
4. Communication /confirmation/conference with surgeon
5. Identification of implant type

If the patient requires any #2-5 above, a separate HIPAA authorization to communicate with LCNI will be completed. For patients who have pre-operative and post-operative research scans at the Slocum Center, data will be stored per standard of care; however, images will be transported through a secure VPN connection for analysis at the [name] Lab.

It is important patient's have pre-operative and post-operative scans on the same MRI machine. The study team will work with the patients and his/her care team to determine the MRI location to best serve the patient's needs.

- **Edema and fluid accumulation in the surgical versus nonsurgical thigh.** From the biopsies, muscle samples will be weighed wet and then dried and weighed again. The difference between the two weights will be used to estimate fluid accumulation in the muscle tissue. Biopsies will be performed in a fasting state.

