Time	-6 mo max	-6 wk to -1 wk (-1 day) ^B	-1 wk (± 0 day)	TKA (Day 0)	1 wk (± 2 days)	2 wk (± 2 days)	5 wk (± 2 days)	6 wk (± 2 days)	
Enrollment and Randomization ¹	X								
Screening ¹	X	X							
Questionnaires ¹		X						X	
Blood Draw ²		X		X		X		X	
MRI ³		X				X		X	
Functional Mobility ⁴		X				X		X	
Strength & Central Activation ⁴		X						X	
3-day food log		X	X	in hosp.	X	X	X		
Accelerometer ^A		X	< -accelerometer on at all times ->				X		
Daily Supplement Ingestion ^{**}			all start	→	→	→		all stop	
Daily Heavy Water Ingestion			all start	→	half stop	half stop			
*Bilateral Biopsy(muscle & fat)				all subjects	half of subjects ⁴	half of subjects ⁴			

¹ Performed at the Slocum Center for Orthopedics and Sports Medicine.

² Performed at PeaceHealth Labs at Sacred Heart Medical Center, RiverBend. Pre-operative bloods collected per standard of care. If pre-operative blood is collected prior to enrollment, study-specific bloods are drawn before initiating study medication (before -1wk). Inpatient draws on day of surgery and post-operative day two.

³ Performed at the Lewis Center for Neuroimaging, University of Oregon. In case of scheduling, mechanical issues, or patient preference, MRIs may be performed at the Slocum Center for Orthopedics & Sports Medicine. Patients must have all study MRI scans on the same machine.

⁴ Performed at the Center for Medical Education and Research, University of Oregon or the Slocum Center.

^A Accelerometer ON daily during waking hours (off while sleeping and showers) including during inpatient hospitalization. Between -6wks to -2 wks wear for 7 consecutive days; -1 week before surgery through 2 weeks post-op, wear for 21 consecutive days; 6 weeks post-op, wear for 7 consecutive days.

^B All pre-operative functional assessments, labs, MRI, strength & central activation, baseline accelerometer and food log must be complete before the subject begins supplement ingestion.

* All subjects will have a single biopsy from each leg in the OR during TKA, while half of subjects will have a single biopsy from each leg at 1 week post and the other half will have a single biopsy from each leg at 2 weeks post. All subjects will only have two biopsies per leg during the entire study. Muscle weight dry versus wet will be compared at 1 or 2 weeks post versus baseline (intraoperative).

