Blood draws (Aim 1 only). The total amount of blood drawn for the purposes of the study will be depend on the study. The potential risks include infection at the site of the blood draw. Careful sterile technique will minimize the chances of infection at the blood draw site. There is a risk for redness, itching, bruising and soreness at the blood draw site. Your blood will be drawn from a site on your arm. Additional blood may be drawn during surgery as determined by the hospital staff and/or doctors outside the purpose of this research study.

Aim 1 (N=40, 20/group) and **Aim 2 (N=80, 40/group)** will have the same total amount of blood drawn, at study intervals.

Muscle biopsy. Biopsies will be collected from all TKA patients (Aim 2 patients will have the choice to participate with or without muscle biopsies).

- **Aim 1 (N=40, 20/group)** will have 1 muscle and 1 fat biopsy per leg during TKA (in the OR) (N=40) and at 1 week post-TKA (N=20); or 2 weeks post-TKA (N=20).
- **Aim 2 (N=80, 40/group)** will have 1 muscle biopsy per leg at Baseline, 6wk & 6mopost-TKA.

The biopsies will be obtained from the vastus lateralis using a 5mm Bergstrom biopsy needle with applied suction under sterile conditions. A single incision of 0.5 cm will be made in the skin down to the level of the fascia, and approximately 150 mg of muscle tissue will be removed during each biopsy.

The potential risks are pain, bleeding, infection, and loss of superficial sensation (light touch, hot/cold) to an area around the biopsy site. There will be a scar approximately 0.6 cm long. The risk of bleeding from the biopsy site is 0.2%; the risk of hematoma is 1.4%; the risk of infection is so small that the precise number is unknown; and the risk of a loss of superficial sensation is 0.5% (55). After the biopsy,

there is a 50% chance that the subject will experience pain at the biopsy site for 24- 48 hrs. However, over the counter pain medications have been successful in mitigating pain from the biopsy site.

Aim 1: It is important to note the biopsies are in a fasting state (no food since dinner the night before). For the first biopsies in the hospital on the day of surgery, fasting is required per routine care before surgery. For the second biopsies, occurring at one OR two weeks after surgery, fasting may lead to some discomfort. Patients may have to delay taking their pain medication, or risk upset stomach if they take their pain medication without food.

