*Data transmitted securely to study team by Slocum Orthopedics. Standard of care instruments are collected by electronic data capture on iPads.

Data Elements Table. Data specifications for data collected through functional tests and study-specific assessments.				
Data Element	Test, Assessment, or Procedure	Collection Method	Description and Intended Use	Specific Aim #
1	Food Log/Diaries	Patient self-report	Caloric intake, stratified by protein, fat, carbohydrate and total calories; Data analysis, stratification, independent covariate.	1
2	Accelerometer	Download of accelerometer data	Patient mobility; Data analysis, stratification, independent covariate.	1
3	Get Up and Go Test	Study staff assessment	Stand from sitting and walk; standardized functional test; study endpoint.	1,2
4	6-minute Walk	Study staff assessment	Standardized functional test; study endpoint.	1,2
5	Stair Climb Up	Study staff assessment	Standardized functional test; study endpoint.	1,2
6	Stair Climb Down	Study staff assessment	Standardized functional test; study endpoint.	1,2
7	Grip Strength – Hand	Study staff assessment	Standardized functional test; study endpoint.	1,2
8	4 meter walk	Study staff assessment	Standardized functional test; study endpoint.	1,2
9	Standing Balance Test	Study staff assessment	Standardized functional test; study endpoint.	1,2
10	Chair Stand Test (Sit to stand five times)	Study staff assessment	Standardized functional test; study endpoint.	1,2
11	MRI; Leg Composition Measurements	Study staff assessment	Bilateral assessment of leg composition; study endpoint.	1
13	Isometric Extensor	Study staff assessment	Bilateral assessment of quadriceps strength; study endpoint.	1
14	Isometric Flexor	Study staff assessment	Bilateral assessment of hamstring strength; study endpoint.	1
15	Essential Amino Acid or Placebo Supplementation Log	Patient self-report	Compliance with study protocol; study intervention.	1,2
16	Muscle & Biopsy	Study staff	Bilateral biopsy; study endpoint(s).	1,2
17	Edema & Fluid Accumulation	Study staff	Bilateral biopsies; controlling for potential confounding of study endpoints.	1,2
#Please refer to the protocol for study-specific lab measurements.				

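### Muscle fluid is estimated from wet minus dry biopsy weight with no denominator, so the size of the tissue piece adds noise to the measure

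*Combined protocol and SAP*

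**What the plan says.** The Aim 1 list of secondary outcomes includes oedema and fluid accumulation in the operated versus the non-operated thigh. The procedure is: "From the biopsies, muscle samples will be weighed wet and then dried and weighed again". The only rule for turning the two weights into a measure follows: "The difference between the two weights will be used to estimate fluid accumulation in the muscle tissue".

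The biopsy footnote to Figure 1 gives the comparison over time: "Muscle weight dry versus wet will be compared at 1 or 2 weeks post versus baseline (intraoperative". It does not say whether that comparison is a difference or a ratio.

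Appendix 1 (table of functional tests and study-specific assessments, item 17) lists the measure for both aims with this intended use: "Bilateral biopsies; controlling for potential confounding of study endpoints".

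On tissue, the muscle biopsy paragraph under Risks says that "approximately 150 mg of muscle tissue will be removed during each biopsy". The Gene Expression paragraph says "RNA will be extracted from 15-20 mg of muscle tissue", and the respiration paragraph uses 5 to 10 mg. No mass is stated for the piece that is weighed wet and dry.

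The oedema item, the footnote and item 17 do not mention a water percentage, a wet/dry ratio or any scaling to tissue mass. Elsewhere the plan does state denominators: blots are expressed relative to total protein and a loading control, and central activation is a ratio. The intention to normalise results statistically refers to mitochondrial respiration.

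**The concern.** A difference of two weights grows with the amount of tissue weighed. A piece twice as heavy, with the same water content, shows twice the apparent fluid. The planned comparisons are between legs and between the intraoperative biopsy and the 1- or 2-week biopsy. Each is a comparison of different pieces, so subtracting one from the other does not remove mass.

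Two uses are affected: the secondary oedema outcome itself, and any adjustment of muscle endpoints for oedema under item 17. A covariate that carries piece-size noise removes less of the confounding that it is meant to remove.

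**Working it through.** The plan gives no SD, power or expected change for this measure, so there is no figure to reproduce. The check is algebra, followed by an illustration under stated assumptions.

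**Algebra.** Let m be the wet mass of a piece and f its water fraction.

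- wet − dry = m × f, which is proportional to m.
- (wet − dry)/wet = f, which is free of m.
- wet/dry = 1/(1 − f), also free of m, but a nonlinear transform of f.

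**Assumptions, none of them in the documents.** f rises from 0.77 to 0.80, with between-sample SD s = 0.015. Mass has the same mean and the same coefficient of variation c at both time points. Mass and water fraction are independent, and so are the two pieces.

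**Standardised paired change.** Mean mass cancels:

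- Water fraction: 0.03 / (0.015 × √2) = 0.03 / 0.0212 = 1.41, whatever c is.
- Raw difference: (f1 − f0) / √[c²(f0² + f1²) + 2s² + 2c²s²], where f0² + f1² = 0.5929 + 0.6400 = 1.2329 and 2s² = 0.00045.

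At c = 10%: 0.01 × 1.2329 + 0.00045 + 0.0000045 = 0.01278. The square root is 0.1131, and 0.03 / 0.1131 = 0.27.

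| Piece-mass CV | Raw difference | Water fraction |
|---|---|---|
| 2% | 0.98 | 1.41 |
| 5% | 0.50 | 1.41 |
| 10% | 0.27 | 1.41 |
| 20% | 0.13 | 1.41 |
| 30% | 0.09 | 1.41 |

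The squared ratio of the two columns is the approximate factor in pairs needed for equal precision: about 2 at a CV of 2%, 8 at 5% and 28 at 10%.

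**Equivalent mass change.** 0.80/0.77 = 1.039. A piece 3.9% heavier with no change in hydration gives the same raw difference as the whole assumed rise.

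**When mass dominates.** To first order, the share of variance due to mass is c² / (c² + CVf²), where CVf = SD of f / 0.77. For an SD of f of 0.01, 0.02 or 0.03, half the variance is due to mass at c of about 1.3%, 2.6% or 3.9%.

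**Plausible piece-mass CV.** The documents give none for the weighed piece. As a rough gauge only, the ranges quoted for other aliquots, if uniform, have CVs of (5/√12)/17.5 = 8% for 15 to 20 mg and (5/√12)/7.5 = 19% for 5 to 10 mg.

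**The case against.** The strongest reply is that the sentence is a short laboratory description and not an analysis definition. A difference used to estimate fluid could still be divided by wet weight later, the Figure 1 footnote could be read as a ratio, and no unit is given. That is possible. But the difference is the only rule stated, and a reader who follows it would not divide. If a ratio is meant, the same one-line change is needed to fix it in advance.

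Other parts of the reply stand and limit the point.

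- **Bias between arms.** A reader might infer that larger pieces would pass for a treatment effect. The trial is described as randomised and blinded, and nothing suggests that piece mass differs by arm. Random mass adds variance. One heavy piece can look like swelling in one subject, but no between-arm bias follows.
- **A useless measure.** A reader might infer that the raw difference mostly reports sample size and cannot detect oedema. That depends on a mass CV that the documents do not give. With pieces matched to about 2%, much of the signal remains. In a second illustration (0.76 versus 0.80 between legs, SD 0.02, 20 pairs, two-sided 0.05), simulated power for the raw difference was 79% at a CV of 5%, against about 100% for the fraction. It fell to 33% at 10% and 12% at 20%.
- **Leftover tissue.** A reader might suppose that the weighed piece is whatever the other assays leave. The documents give no order of allocation, so this is not established.
- **Oedema otherwise uncontrolled.** In Aim 1, "T1 & T2 weighted MR images will be used to quantify quadriceps volume vs. edema". Figure 1 places MRI pre-operatively and at 2 and 6 weeks, but not at 1 week, when half the subjects have their post-operative biopsy. Aim 2 has no MRI.
- **Effect on the main analyses.** The covariates named under Power analyses do not include biopsy fluid. No numbered research question and no power figure concerns oedema. Item 17 states an intended use without naming a model.

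**Conclusion.** The point holds as a defect in how one biopsy measure is defined. As written, the estimate of muscle fluid scales with piece mass, no passage fixes that mass or divides by it, and comparing legs or visits does not cancel it. The result is lost precision in a secondary outcome and in any adjustment made under item 17.

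The proportionality is certain; the size of the loss is not. Under the assumed water fractions and SD, the standardised change falls from 1.41 to between 0.98 (mass CV 2%) and 0.09 (mass CV 30%). The documents support neither a claim of between-arm bias nor a claim that the measure carries no information. They do not show that the primary outcomes are affected unless the measure is used to adjust them. The change is worth making because it is nearly free.

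**What to change.** In the oedema item of the Aim 1 secondary outcomes, replace the sentence on the difference of the two weights with:

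> Water fraction, (wet − dry)/wet weight, will be computed for each leg and time point and used to estimate fluid accumulation.

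Use the same quantity for the comparison in the Figure 1 footnote and wherever item 17 of Appendix 1 is used for adjustment, in either aim. Name one scale in advance: the wet/dry ratio is also free of piece mass, but comparisons of means can differ between the two scales.

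The cost is wording and a recalculation. Both weights are already part of the procedure, so no new tissue or visits are needed. The Aim 2 website text says that the first part of the study was completed in 2016, so for Aim 1 the change means recomputing the measure from stored data wherever both weights were kept.

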Biochemistry. Recent studies in the [name] Laboratory have generated exciting preliminary results showing essential amino acid (EAA) supplementation attenuates quadriceps atrophy and accelerates the return of functional mobility following TKA (37). For patients on EAA, quadriceps atrophy was only -6% & -3% in the operative and non-operative quadriceps, respectively, six weeks after TKA but -18% & -10%, respectively, in patients on Placebo (a 3-fold difference). Of clinical relevance, these patients on EAA were able to maintain strength and demonstrated an accelerated return of functional mobility vs. Placebo, 6 wk post-TKA. At the cellular level, our preliminary results show that EAA supplementation

down-regulated catabolic signaling (FoxO3a) and up-regulated amino acid transporter (SLC36A2), regulated in development and DNA damage response (REDD1) and activating transcription factor 4 (ATF4) expression vs. Placebo. While studies by others have linked these molecules with the insulin like growth factor (IGF-I) and vascular endothelial growth factor (VEGF) (i.e., angiogenesis) pathways, whether they are directly stimulated by EAA supplementation in a clinical population remains unknown. We interpret these positive changes at the cellular level to be responsible for the reduction in muscle loss and, preservation of strength, and explain the acceleration of the return of functional mobility.

Our preliminary fractional synthesis data (FSR) show that older adults respond appropriately to acute ingestion of 20 g of EAA (i.e., similar response to young healthy controls). We also have preliminary FSR data showing that basal rates of muscle protein synthesis are similar between TKA patients ($0.0563 \pm 0.008\%$ /hour) and older healthy control subjects ($0.0566 \pm 0.008\%$ /hour). What is not known is what effect TKA has on muscle protein synthesis and breakdown in response to chronic EAA supplementation (for 1 week prior to, and for 6 weeks post-TKA). We have extensive experience with stable isotope tracer methods to determine fractional synthesis rates (FSR), a direct measure of muscle protein synthesis (31-35, 39-41, 50, 113, 114). However, in order to determine mechanisms, and link cellular changes in anabolic and catabolic pathways with atrophy (Placebo) and atrophy prevention (EAA) we must also quantify muscle protein breakdown.

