- **Function.** Standardized grip strength, standing balance, chair stand test, timed up-and-go (TUG), timed stair ascent and timed stair descent, 4 meter walk test and the 6 minute walk will be assessed. Grip strength will determine changes in each hand grip over time. Standing balance will measure changes over time in balance. The chair stand test measures the time it takes for

the subject to stand and sit five times. TUG will measure the time (seconds) needed to stand from a chair, walk 3 meters, turn around, walk back and be seated again. Timed stair ascent (10 steps) and descent will be recorded. The 4 meter walk will tell us how long it takes you to walk a short distance (4 meters) while the 6 minute walk will measure the distance you can walk over a longer distance (total distance in 6 minutes). We have experience with these functional measures. Each functional mobility measure will be performed on a single standardized chair (TUG) and stairs. Functional assessments will not be performed in a fasting state. Functional measurements may be performed at either the [name] Lab on the University of Oregon campus or the Slocum Center for Orthopedics & Sports Medicine.

- **Strength & central activation deficit.** Co-Investigator [name], PhD, will contribute her expertise to quantify pre- and post-operative changes in strength and quadriceps activation (24). Strength will be quantified using a Biomed +/- tests for central activation deficits (CAD). CAD contributes to early weakness following TKA, and [name] will quantify this progression between groups over time using previously published methods will be followed (23, 44, 62, 65, 67, 112). Voluntary activation of the knee extensor muscles will be assessed through the painless method of supramaximal magnetic stimulation of the femoral nerve superimposed on the MVC (90). Central activation of the knee extensors will be calculated from the resulting force as follows: $(MVC/(MVC + Stimulation)) \times 100$ (65). Nerve function will be determined using the latency of the M-wave in response to supramaximal magnetic stimulation of the femoral nerve (23, 44). Additionally, pre-post surgery measures of the area of the negative peak of the M-wave will be used to estimate motor neuron loss (67). Strength and central activation deficits will not be performed in a fasting state. Central activation is measured on the University of Oregon campus or at the Slocum Center.

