Power analyses. For our power calculations, we have assumed a Type I error rate (α) of $.05$, two-tailed. We based power calculations on effect sizes (d) that we derived from analysis of preliminary data preliminary data and prior studies (10, 30, 32, 33, 36, 41, 51, 113). We calculated d as the standardized mean difference between treatment conditions at follow-up: $d = (x_C - x_T)/S$, where x_C represents the primary outcome mean in the Placebo and EAA conditions and S is the pooled standard deviation, after adjusting x for pretest scores and covariates (sex, tourniquet time, age, body mass index, fat/carbohydrate/protein intake).

We propose to enroll **40 total subjects for Aim 1** who are retained through protocol completion (20/group, EAA and Placebo, randomized to either 1 week or 2 week post-operative biopsies), and **80 total subjects** (40/group, EAA and Placebo) **for Aim 2** who are retained through protocol completion to account for possible attrition and to ensure sufficient power to test the hypotheses that EAA therapy up-regulates basal levels of muscle protein synthesis, and reduces post-operative atrophy bilaterally, preserves quadriceps strength, and improves functional mobility relative to a Placebo condition.

Effect sizes. Effect sizes were as follows: (a) Cell and FSR data: REDD1 $d = 1.24$, SLC36A2 $d = 1.27$, and FSR $d = 1.51$ (FSR calculated from mean change from baseline). The mean effect across outcomes was $d = 1.37$, reflecting large effects. (b) Physiological and functional data (percent change from Baseline to 6 wk): operative quadriceps volume $d = 1.52$, and isometric strength $d = .90$; non-operative quadriceps volume $d = 1.05$, and isometric strength $d = .66$; timed up-and-go test $d = 1.03$, timed stair ascent $d = 1.08$, timed stair descent $d = 1.13$, and six-minute walk test $d = .70$. Mean effect size was $d = 1.01$, reflecting large effects.

Power calculations. Power calculations were based on the sample size and minimally detectable ES (MDES) as follows:

- **Aim #1:** For a sample size of 20 completed subjects/group (10/group for metabolic studies, however, EAA vs. Placebo = 20 total EAA and 20 total Placebo). Aim 1, proposed study can detect

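### M-wave area is to be read as motor neuron loss, but it is a muscle response, so the quadriceps atrophy this trial expects could be misread as neuron loss, and an arm difference in atrophy as neuron sparing by EAA

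*Combined protocol and SAP*

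**What the plan says.** The measure is in the Strength & central activation deficit bullet of Secondary Outcome Measures, Aim 1. Two readings are taken from the M-wave. Latency is the nerve measure: "Nerve function will be determined using the latency of the M-wave in response to supramaximal magnetic stimulation of the femoral nerve". Area is given a cellular meaning: "pre-post surgery measures of the area of the negative peak of the M-wave will be used to estimate motor neuron loss". The bullet states no scaling to muscle size, no allowance for swelling and no caveat. Its between-arm statement, "will quantify this progression between groups over time", is about central activation deficit, not M-wave area.

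Other sections bear on this:

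- Preliminary Studies (Biochemistry) reports for EAA that "quadriceps atrophy was only -6% & -3% in the operative and non-operative quadriceps", and larger losses "six weeks after TKA but -18% & -10%, respectively, in patients on Placebo".
- The Aim 1 schedule (Figure 1) puts strength and central activation testing before surgery and at 6 weeks, and MRI before surgery and at 2 and 6 weeks.
- The Muscle volume bullet says "T1 & T2 weighted MR images will be used to quantify quadriceps volume vs. edema".
- The covariates named under Power analyses (sex, tourniquet time, age, body mass index, diet) include neither quadriceps volume nor edema.
- Appendix 1 lists biopsy fluid content as a control for confounding in general. Aim 1 biopsies end at 1 or 2 weeks, so they do not cover the 6-week M-wave.

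**The concern.** The M-wave is what a muscle returns when its nerve is fully stimulated. Its area can fall because fewer motor axons respond, because the responding fibres are smaller, or because fluid between muscle and electrode weakens the signal. This is general electrophysiology and is not stated in the documents. What makes it matter is the trial's own premise: both quadriceps shrink by the visit at which area is remeasured, and they shrink less on EAA.

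Two errors become possible. Within either arm, atrophy alone could be recorded as motor neuron loss. Between arms, preserved muscle on EAA could be described as preserved motor neurons. In a trial whose stated purpose is mechanism, either would be an unsupported mechanistic statement. It would also blur the distinction between muscle loss and neural deficit that this testing is meant to draw.

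**Working it through.** The plan gives no effect size, SD, power or test for M-wave area, so there is no stated figure to reproduce. The check asks what the stated reading would return if no motor neuron were lost in either arm.

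**Inputs from the documents.** Six-week quadriceps loss is 18% (Placebo) and 6% (EAA) in the operative leg, and 10% and 3% in the other leg (Preliminary Studies). Aim 1 has 20 completers per arm and a two-sided alpha of .05 (Power analyses).

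**Inputs assumed.** The fall in M-wave area per 1-point fall in volume is k = 0.25 to 1. The SD of percent change in area is 7.9 to 30 points. The lower end borrows the SD implied for operative quadriceps volume: 12 / 1.52 = 7.9, pairing the 12-point preliminary difference with the plan's effect size for that outcome. The documents give neither k nor the SD for M-wave area.

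**Step 1: apparent loss within each arm, operative leg.** Apparent loss = k × volume loss.

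- k = 1: 18% on Placebo, 6% on EAA.
- k = 0.5: 9% and 3%.
- k = 0.25: 4.5% and 1.5%.

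**Step 2: apparent arm difference.** Operative leg: k × (18 − 6) = 12k points. Non-operative leg: k × (10 − 3) = 7k points. Using the non-operative leg as a control, which the plan does not specify for this measure, would not remove the difference: (18 − 10) − (6 − 3) = 5 points at k = 1.

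**Step 3: chance of a nominally significant result favouring EAA, if the arms were compared.** A two-sample t test stands in for the plan's ANCOVA. The noncentrality is (12k / SD) × √(20/2), with 38 degrees of freedom. The chance is the upper-tail probability beyond the two-sided .05 critical value. With no bias it is 2.5%. Two examples:

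- k = 0.5, SD 20: 6/20 = 0.30; 0.30 × √10 = 0.95; chance 15%.
- k = 1, SD 15: 12/15 = 0.80; 0.80 × √10 = 2.53; chance 69%.

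| k | Gap (points) | SD 7.9 | SD 10 | SD 15 | SD 20 | SD 30 |
|---|---|---|---|---|---|---|
| 0.25 | 3 | 21.5% | 15.0% | 9.0% | 6.7% | 4.9% |
| 0.5 | 6 | 64.8% | 45.6% | 23.4% | 15.0% | 9.0% |
| 0.75 | 9 | 93.9% | 79.2% | 45.6% | 28.3% | 15.0% |
| 1 | 12 | 99.7% | 95.9% | 69.3% | 45.6% | 23.4% |

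Twenty per arm is an upper limit for this measure. Under Adequacy of Protection Against Risks, magnetic stimulation is withheld from anyone with a positive answer on its safety screen.

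**Step 4: swelling.** The plan measures edema but nowhere predicts that it differs by arm. Equal swelling would shift both arms' pre-post change or add noise. It adds to the within-arm misreading but does not create an arm difference.

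**The case against.** A reader might infer that the trial will report an effect of EAA on motor neurons. The documents do not go that far. None of the Aim 1 or Aim 2 study questions concerns motor neurons, Data Analysis names no M-wave outcome or test, and Appendix 1 has no M-wave entry. What stands is that the result could be misread in this way: the measure sits among secondary outcomes of a two-arm trial, and the written interpretation is already motor neuron loss.

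A reader might also take one cell of the table as the false-positive rate. The documents support no single cell, because k and the SD are both assumed.

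The method is attributed to published work. The source cited for this reading is, by its title, a study of unilateral femoral neuropathies. Whether it handles muscle size cannot be seen from here. The protocol carries over no such step, and it applies the reading where atrophy is the expected finding.

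An obvious remedy would be to allow a motor-neuron statement only if the arm difference survives adjustment for same-visit quadriceps volume. The objection to that is sound. Volume is measured after randomization, EAA is meant to change it, and true denervation would shrink it too. Adjustment could erase a real neural effect and would not isolate one.

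Finally, the measure is ancillary. Aim 1 secondary outcomes are described as preliminary data to inform Aim 2, and Aim 2 drops this testing. The Aim 2 website text says the first part of the study was completed in 2016. This limits the importance of the point, but the interpretation still governs how Aim 1 results are described.

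**Conclusion.** The point holds as one of interpretation. The plan assigns a change in M-wave area to motor neuron loss, which that measure cannot establish alone, in a trial that expects muscle to shrink, and to shrink unequally by arm, at the same visit. If area follows volume at all, the error in an arm comparison favours EAA whenever EAA preserves muscle.

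Its size cannot be derived from the documents. Across the assumed inputs it runs from negligible (4.9% against 2.5% with no bias) to dominant (99.7%). This rests on the general premise that M-wave area depends on fibre size, on the preliminary atrophy figures recurring, and on 20 tested per arm. An arm difference in swelling is not supported. The consequence is confined to one ancillary Aim 1 secondary measure, and no primary conclusion is affected.

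**What to change.** In the Strength & central activation deficit bullet, change the end of the M-wave area sentence so that the pre-post measures *will be reported as M-wave area*. Add that a fall, or a difference between arms, will not be described as motor neuron loss or sparing on this measure alone.

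Report the area beside MRI quadriceps volume and edema for the same leg at baseline and 6 weeks, as descriptive context only. Do not make a volume-adjusted test the condition for a motor-neuron claim. Keep latency as the stated nerve-function measure.

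The cost is a wording change and a descriptive table. MRI is already scheduled at both time points, so no new data are needed. The trial gives up a motor-neuron claim from this measure.
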